1. LIST OF ABBREVIATIONS

ADR	Adverse Drug Reaction
AE	Adverse Event
ATC	Anatomical Therapeutic Chemical
bd	Two times a day
CFDA	China Food and Drug Administration
eCRF	Electronic Case Record Form
FP	Futicasone propionate
GCP	Good Clinical Practice
GCSP	Global Clinical Safety and Pharmacovigilance
GSK	GlaxoSmithKline
HFA	Hydrofluoroalkane
ICH	International Conference on Harmonization
IEC	Independent Ethics Committee
IRB	Institutional Review Board
MedDRA	Medical Dictionary for Regulatory Activities
pMDI	Pressurized Metered-Dose Inhaler
qds	Four times a day
SAE	Serious Adverse Event
SADR	Serious Adverse Drug Reaction
SCG	Sodium Cromoglycate
WHO	World Health Organisation
µg	Microgram

Trademark Information

Trademarks of the GlaxoSmithKline group of companies	Trademarks not owned by the GlaxoSmithKline group of companies
FLIXOTIDE	None

3. ABSTRACT

Rationale

Flixotide administered via a pressurized metered-dose inhaler (pMDI) formulated with the propellant hydrofluoroalkane (HFA) was approved in China in 2002 with the strength of 50, 125 and 250 µg of fluticasone propionate per actuation. It was indicated for prophylactic treatment of asthma, including adults, adolescents older than 16 years of age and children aged 4 to 16 years and has demonstrated a positive benefit/risk profile in Chinese patients.

In Nov 2016, China Food and Drug Administration (CFDA) approved the therapeutic use of Flixotide 50 µg (recommended dosing 50 to 100 µg twice daily inhaled via a paediatric spacer device with a face mask) in children aged 1 to <4 years, with a requirement for GlaxoSmithKline (GSK) to conduct proactive safety monitoring in this population. To meet CFDA requirement, GSK will initiate this post-marketing safety monitoring program to evaluate the safety of Chinese patients aged 1 to <4 years when using Flixotide 50 µg via a paediatric spacer device with a face mask in clinical practice. It is anticipated that the obtained data from this post-marketing program will further enhance and supplement the currently available safety data from clinical trials as well as provide more detailed information than that obtained typically available through routine spontaneous adverse event reporting.

Objective

The objective of this program is to evaluate the post-marketing safety profile of Flixotide 50 µg inhaled via a paediatric spacer device with a face mask in patients aged 1 to <4 years. The adverse drug reactions and predictors of these adverse reactions among patients will be observed.

Study Design

This is an observational study with no medical interventions. Subjects (children aged 1 to <4 years) information that is pre-defined in the protocol will be collected in the electronic case record form (eCRF). The decision to prescribe Flixotide 50 µg will not be influenced by whether or not to participate in this observational program.

The observational program will include subjects who have been prescribed Flixotide 50 µg (recommended dosing 50 to 100 µg twice daily inhaled via a paediatric spacer device with a face mask) for appropriate medical use for the first time. The subjects who have been exposed to Flixotide 50 µg, 125 µg and 250 µg previously will not be included.

The maximum program duration will be 12 weeks with 3 visits. Visit1 (Day 1) is the start of the observational program. The follow-up visits will be scheduled at 4 weeks (Visit 2), and 12 weeks (Visit 3). Unless subjects discontinue Flixotide 50 µg treatment or withdraw their consent for continued data collection, subjects will remain in the program until Visit 3.

This post-marketing program is planned to recruit paediatric subjects from 3 to 5 hospitals (may be adjusted as per recruitment progress) in China. It is planned to include 150 asthmatic subjects, aged 1 to <4 years who have been prescribed Flixotide 50 µg treatment for appropriate medical use for the first time in China.

4. AMENDMENTS AND UPDATES

None.

5. MILESTONES

Milestone	Planned date
Start of data collection	31-Aug-2017
Study progress report	30-Sep-2017
End of data collection	30-Aug-2018
Final report of study results	31-Oct-2018

6. RATIONALE AND BACKGROUND

6.1. Background

Fluticasone Propionate Inhaled Aerosol (Flixotide™) is the brand-name product of GlaxoSmithKline (GSK) Group. Flixotide is an established inhaled corticosteroid which has been approved worldwide for use in the prophylactic treatment of mild, moderate and severe asthma in adults (maximum daily dose of 2000 µg/day) and children aged 4 to 16 years (maximum daily dose of 400 µg/day). For children aged 1 to <4 years, Flixotide is currently registered for the treatment of asthma (100 to 200 µg/day) in East Asian markets including Hong Kong, Taiwan and Korea, as well as some countries in South East Asia and the West. Similar clinical pharmacology data was obtained for subjects aged 1 to <4 years compared to subjects aged 4 to 11 years and adults for fluticasone propionate (FP) pMDI 100 µg bd [GlaxoSmithKline Document Number [YM2002/00005/00](#), 2002].

Data presented in the [Module 2.5, [Fluticasone propionate](#). 2013], from both clinical trials and the published literature have shown that the Flixotide 50 µg can provide similar benefits in terms of enhanced lung function, decreased symptoms and an acceptable safety profile [Module 2.5, [Fluticasone propionate](#). 2013]. In the global development program, a total of 703 subjects aged 1 to <4 years from the four key studies FAS30007 [GlaxoSmithKline Document Number [GM2001/00151/00](#)], FAS30009 [GlaxoSmithKline Report Number [GM2001/00103/00](#)], FLTB3016 [GlaxoSmithKline Report Number [GM1996/00034/00](#)] and FLTB3017 [GlaxoSmithKline Report Number [GM1996/00033/00](#)] received FP pMDI 100 µg bd for up to 12 or 52 weeks; this is calculated to be equivalent to 469 subject-years [GlaxoSmithKline Document Number [YM2002/00005/00](#), 2002]. The safety profile has been summarized as below:

- The majority of adverse events (AEs) reported during the clinical programme were primarily from the ear, nose and throat and lower respiratory body systems; typical for this subject population. No new or unexpected events were identified.
- A higher percentage of subjects aged <2 years experienced AEs during treatment than did those aged ≥2 years.

- In the 52-Week study (FAS30009), there was no apparent evidence of any important clinical differences in the AEs occurring before and after Day 175, nor any evidence to suggest increasing rates of AEs in either the FP 100 µg bd or sodium cromoglycate (SCG) 5 mg qds treatment group after Day 175.
- Drug-related AEs were uncommon and not of clinical concern. The incidence of subjects withdrawing due to an AE was low. The incidence of serious adverse events (SAEs) was low, none were attributable to FP treatment and there were no deaths.
- A single incident of cataract was reported in subjects treated with FP 100 µg bd out of a total subject population of 703 and one further case was identified in a steroid naïve subject at Screening.
- FP 100 µg bd treatment for 52 weeks in children aged 1 to <4 years had no negative effect on growth compared to SCG.
- Serum/urinary cortisol levels generally reduced in subjects receiving FP 100 µg bd. Two subjects that received FP 100 µg bd in FAS30009 shifted from normal to low serum cortisol levels. No cortisol changes were associated with symptoms of adrenal insufficiency.
- No changes in clinical chemistry or haematology measurements examined were of clinical concern. There was no apparent evidence that treatment with FP 100 µg bd had any effects on vital signs and physical examinations. Incidence of oral candidiasis was uncommon.
- The SAEs reported from the studies were consistent with the known safety profile of FP, as established in the original Marketing Authorisation Application and variations. No new safety concerns, specific to the use of FP in a 1 to <4 year-old subject population were identified.

Overall, FP 100 µg bd was at least as well tolerated as placebo and the active comparator (SCG) in children 1 to <4 years old [for details please refer to Module 2.5, [Fluticasone propionate](#). 2013]. The risk: benefit profile of FP 100 µg bd in the treatment of asthma in paediatrics aged 1 to <4 years old has been preferable.

In addition, GSK Global Clinical Safety and Pharmacovigilance (GCSP) regularly reviews the literature relating to matters of safety, and maintains a database of spontaneously reported AEs and literature references. In the recent [[Periodic Benefit Risk Evaluation Report](#), 2016], it is concluded that benefit profile of FP in authorized indications continues to be positive; also there is no significant change to the risk profile.

6.2. Rationale

Flixotide administered via a pressurized metered-dose inhaler (pMDI) formulated with the propellant hydrofluoroalkane (HFA) was approved in China in 2002 with the strength of 50, 125 and 250 µg of FP per actuation. It was indicated for prophylactic treatment of asthma, including adults, adolescents older than 16 years of age and children aged 4 to 16 years and has demonstrated a positive benefit/risk profile in Chinese patients.

In Nov 2016, China Food and Drug Administration (CFDA) approved the therapeutic use of Flixotide 50 µg (recommended dosing 50 to 100 µg twice daily inhaled via a paediatric spacer device with a face mask) in children aged 1 to <4 years, with a requirement for

GSK to conduct proactive safety monitoring in this population. To meet CFDA requirement, GSK initiates this post-marketing safety monitoring program to evaluate the safety of Chinese patients aged 1 to <4 years when using Flixotide 50 µg via a paediatric spacer device with a face mask in clinical practice.

7. RESEARCH QUESTION AND OBJECTIVE(S)

The data obtained from this post-marketing program will further enhance and supplement the currently available safety data from clinical trials as well as provide more detailed information than that obtained typically available through routine spontaneous adverse event reporting, thus justify the safety use of Flixotide 50 µg inhaled via a paediatric spacer device with a face mask in Chinese children aged 1 to <4 years old.

The objective of this program is to evaluate the post-marketing safety profile of Flixotide 50 µg in patients aged 1 to <4 years. The adverse drug reactions and predictors of these adverse reactions among patients will be observed. The primary goals of this program are listed below:

1. To observe the incidence of known adverse reactions in children aged 1 to <4 years.
2. To observe the occurrence of unexpected adverse reactions in children aged 1 to <4 years.

8. RESEARCH METHODS

8.1. Study Design

This is a single arm observational study with no medical interventions. Subjects (children aged 1 to <4 years) information that is pre-defined in the protocol will be collected in the electronic case record form (eCRF). The decision to prescribe Flixotide 50 µg (recommended dosing 50 to 100 µg twice daily inhaled via a paediatric spacer device with a face mask) will not be influenced by whether or not to participate in this observational program.

The observational program will include subjects who have been prescribed Flixotide 50 µg (recommended dosing 50 to 100 µg twice daily inhaled via a paediatric spacer device with a face mask) for appropriate medical use for the first time. The subjects who have been exposed to Flixotide 50 µg, 125 µg and 250 µg previously will not be included.

The maximum program duration will be 12 weeks with 3 visits. Visit1 (Day 1) is the start of the observational program. The follow-up visits will be scheduled at 4 weeks (Visit 2), and 12 weeks (Visit 3). Unless subjects discontinue Flixotide 50 µg treatment or withdraw their consent for continued data collection, subjects will remain in the program until Visit 3.

Visit1 is an on-site visit where subjects have been prescribed Flixotide 50 µg for appropriate medical use. The following procedures/assessments will be performed and recorded during Visit1:

- Obtain written informed consent
- Verification of inclusion criteria
- Obtain the demographic information
- Obtain the medical history
 - Disease history: asthma disease history and other systemic severe disease assessed by investigator.
- Collect concomitant medication use
 - Asthma treatment medication within 30 days prior to Visit 1.
 - Other important medications for severe disease treatment in the past 1 month.
- AEs and SAEs

Visit 2 and Visit 3 are follow-up visit. The follow-up can be conducted on site or by telephone based on the decision made by qualified medical staff. The following assessments will be performed at Visit 2 and Visit3:

- AEs and SAEs
- Collect Flixotide 50 µg treatment information
- Review concomitant medication use

Time and Events Table ([Table 1](#)) provides an outline of the information that will be collected on subjects who have provided consent for data collection according to local ethical guidelines for observational program. Visit 1 is an on-site visit; Visit 2 and Visit 3 are follow-up visits which can be conducted on site or by telephone.

Table 1 Time and Events Table

Procedure	Visit Number			
Visit (Visit Window)	1 ¹ Day1	2 4Ws ±3d	3 12Ws±3d	Early Withdrawal
Informed consent	×			
Demographic data	×			
Medical history	×			
Flixotide 50 µg therapy ²	×	×	×	×

Procedure	Visit Number			
Visit (Visit Window)	1 ¹ Day 1	2 4Ws ±3d	3 12Ws±3d	Early Withdrawal
Concomitant medication	×	×	×	×
Adverse Event ³	×	×	×	×
Serious Adverse event ³	×	×	×	×
Diary card dispense ⁴	×			

1. Visit 1 marks the start of the observational period.
2. Change in drug dosage, discontinuation or resumption and reasons for these changes, and compliance of Flixotide 50 µg therapy.
3. SAEs will be recorded from the time the consent form is signed through Visit 3; AEs will be recorded from the start of Flixotide 50 µg treatment through Visit 3.
4. Paper diary cards will be dispensed at Visit 1 for the parent/guardian of the subject to record Flixotide 50 µg therapy, concomitant medication, AEs and SAEs. The investigator will record the source information in the medical records by asking the parent/guardian of the subject during the follow-up on site or telephone visits.

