8.5.2. Timings of Assessment during follow-up

Visit 1 will be defined as baseline. Follow-up visits will be performed at 4 weeks and 12 weeks since baseline visit. There is ± 3 day window period for every follow up visit.

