12. APPENDICES

12.1. Appendix 1 Non-Serious Adverse Events/Adverse Drug Reaction (AE/ADR) Pages

CONFIDENTIAL

NON-SERIOUS ADVERSE EVENTS (AE) (Page 1 of 4)

DEFINITION OF A NON-SERIOUS ADVERSE EVENT (AE)

Any untoward medical occurrence in a patient or clinical investigation subject, temporally associated with the use of a medicinal product, whether or not considered related to the medicinal product.

An AE can therefore be any unfavorable and unintended sign (including an abnormal laboratory finding), symptom, or disease (new or exacerbated) temporally associated with the use of a medicinal product. For marketed medicinal products, this also includes failure to produce expected benefits (i.e., lack of efficacy), abuse or misuse.

Examples of an AE include:

- Exacerbation of a chronic or intermittent pre-existing condition including either an increase in frequency and/or intensity of the condition.
- New condition(s) detected or diagnosed after GSK product administration even though it may have been present prior to the start of the study.
- Signs, symptoms, or the clinical sequelae of a suspected interaction.
- Signs, symptoms, or the clinical sequelae of a suspected overdose of either GSK product or a concomitant medication (overdose *per se* should not be reported as an AE/SAE).

Examples of an AE do NOT include a/an:

- Medical or surgical procedure (e.g., endoscopy, appendectomy); the condition that leads to the procedure is an AE.
- Situations where an untoward medical occurrence did not occur (social and/or convenience admission to a hospital).
- Anticipated day-to-day fluctuations of pre-existing disease(s) or condition(s) present or detected at the start of the study that do not worsen.
- The disease/disorder being studied, or expected progression, signs, or symptoms of the disease/disorder being studied, unless more severe than expected for the subject's condition.

For GSK clinical studies, AEs may include pre- or post-treatment events that occur as a result of protocol-mandated procedures (i.e., invasive procedures, modification of subject's previous therapeutic regimen). See protocol for clarification.

IF THIS EVENT MEETS THE DEFINITION OF SERIOUS, COMPLETE THE SERIOUS ADVERSE EVENT SECTION

IDSL Version 07.02 - 26 APR 16 [AE]

CONFIDENTIAL

NON-SERIOUS ADVERSE EVENTS (AE) (Page 2 of 4)
MONITOR DATA VALIDATION CHECKS

- Check that either 'Yes' or 'No' box at the top of the page has been completed.

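### Visit 1 requires no record of non-severe conditions, so mild complaints that pre-date the first dose may be misclassified when adverse reactions are counted

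*Combined protocol and SAP*

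**What the plan says.** **Baseline.** Section 8.5.2 states: "Visit 1 will be defined as baseline". For that visit, section 8.1 asks for "Disease history: asthma disease history and other systemic severe disease assessed by investigator". Prior medication has two parts: "Asthma treatment medication within 30 days prior to Visit 1" and "Other important medications for severe disease treatment in the past 1 month". Table 1 and section 8.4 refer only to medical history in general and add nothing wider. No examination or symptom check is scheduled at Visit 1.

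**Event collection.** A footnote to Table 1 says "AEs will be recorded from the start of Flixotide 50 µg treatment through Visit 3". For Visits 2 and 3, "The follow-up can be conducted on site or by telephone". Parents receive a paper diary card at Visit 1.

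**What counts as an AE.** Appendix 1 includes among its examples "New condition(s) detected or diagnosed after GSK product administration even though it may have been present prior to the start of the study". The same page excludes expected fluctuation of a condition that existed or was found at study start and has not become worse.

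**Analysis.** Section 8.6.4 summarises AEs that occur while the child is on Flixotide 50 µg. Its main estimate is the share of the safety population with any drug-related AE. It gives no rule for comparing an event with the child's state at Visit 1.

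**The concern.** The study has one arm, so no comparator group absorbs the background of minor complaints in children aged 1 to under 4. The child's own condition before the first dose is the only reference, and for anything short of severe systemic disease the protocol does not ask for it.

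Oral candidiasis, which section 6.1 mentions as an uncommon finding, shows the difficulty. Suppose a child has a mild mouth complaint on Day 1 and a parent mentions it at Week 4. The site may have nothing written down that shows whether it came before or after the first dose. The error can run either way: a complaint that was already there may be recorded as new and then judged related, or a real reaction may be set aside because nobody can show that it was new.

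Both errors fall on the first primary goal in section 7, the incidence of known reactions, and on the ADR frequency in section 8.6.4.

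**Working it through.** **1. The plan's own figure.** Section 8.6.2 gives N = 150, an ADR rate of 1.5%, and about a 90% chance of seeing at least one ADR.

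1 − (1 − 0.015)^150 = 1 − 0.985^150 = 0.896.

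The figure reproduces, and this point does not dispute it.

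**2. Expected count.** 150 × 0.015 = 2.25 children with an ADR. At 3%, the lowest study rate that section 8.6.2 cites, 150 × 0.03 = 4.5.

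**3. Weight of one child.** 1/150 = 0.67 percentage points, which is 0.67/1.5 = 44% of the assumed rate, in either direction. With exact 95% intervals:

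- 2 of 150: 1.33% (0.16% to 4.73%)
- 3 of 150: 2.00% (0.41% to 5.73%)

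**4. Tracing a mild complaint present on Day 1.**

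- *Visit 1 history and medication:* not required, because the complaint is neither asthma nor severe systemic disease.
- *Pre-dose AE record:* none for a non-serious complaint, because AE recording starts with treatment.
- *Appendix 1 exclusion:* applies in principle, but there is no Day 1 entry to check it against.
- *AE start date:* the form wants the date of first occurrence and accepts a best estimate.
- *ADR form, section 5:* asks for relevant conditions and their onset, but the form is completed only once the event has been judged related.

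**5. Possible size.** The documents give neither the prevalence of such complaints nor the share that would be judged related. Both inputs below are assumptions. Let p be the proportion of children with an unrecorded look-alike complaint and a the proportion of these judged drug related.

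False ADR children = 150 × p × a.

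Apparent rate = 1 − (1 − 0.015)(1 − p × a), taking true and false reactions as independent.

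| p | a | False ADR children per 150 | Apparent rate when the true rate is 1.5% |
|---|---|---|---|
| 1% | 10% | 0.15 | 1.60% |
| 1% | 50% | 0.75 | 1.99% |
| 5% | 10% | 0.75 | 1.99% |
| 5% | 25% | 1.88 | 2.73% |
| 10% | 10% | 1.50 | 2.49% |
| 10% | 50% | 7.50 | 6.43% |

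The table covers only the upward error. Dismissed reactions would pull the other way and cannot be sized from the documents either.

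**The case against.** The plan has real safeguards.

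- Appendix 1 says that a condition present at the start that has not worsened is not an AE.
- A start date is mandatory, so a complaint known to pre-date treatment should carry a pre-dose date.
- The suggested follow-up question in section 10.1.1.1 asks about problems since the last contact.
- The diary card gives parents somewhere to note events as they happen.
- An AE becomes an ADR only if the investigator judges it related, after weighing concurrent illness and history.

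The study is also descriptive, and the interval around 2 of 150 is far wider than a one-child shift.

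Most of this stands, and it limits the size. It does not close the gap. The start date and the exclusion are only as good as what someone remembers about Day 1. The diary begins at Visit 1 and is not described as recording what was already there. The causality judgement calls for history that the protocol does not require for non-severe conditions. A wide interval describes sampling error and does not correct misclassification.

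A reader might infer more than the documents support in four respects:

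- *That any Day 1 complaint mentioned later automatically becomes a new ADR.* The exclusion, the start date and the relatedness judgement all stand in the way.
- *That children switching from another inhaled steroid go unnoticed.* Asthma treatment in the prior 30 days is recorded, so the medication gap concerns treatments for non-severe, non-asthma conditions.
- *That the cataract history in section 6.1 proves the point.* The text says only that "one further case was identified in a steroid naïve subject at Screening". It does not say how that case was classified or why.
- *That every carried-in complaint would be judged related.* Nothing in the documents suggests this, which is why the table applies a relatedness fraction.

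**Conclusion.** The gap is real. Non-severe conditions and their treatments have no required record before the first dose, and the safeguards that remain depend largely on recall after the event. A pre-existing complaint may be counted as an AE and, if judged related, as an ADR, or a true reaction may be discounted.

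The size is unknown. What is firm is the leverage: 0.67 percentage points per misclassified child, against 2.25 expected children with an ADR at the plan's 1.5%. The range of 0.15 to 7.5 false ADR children, or an apparent 1.6% to 6.4%, rests wholly on the assumed 1% to 10% prevalence and 10% to 50% relatedness. It shows sensitivity and is not a forecast. The sample size and the 90% figure are unaffected.

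This is an inexpensive improvement that should be made, not a flaw that invalidates the study.

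**What to change.** At the on-site Visit 1, after consent and before the first dose:

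1. Ask the parent an open question of the kind already given in section 10.1.1.1.
2. Record every ongoing sign, symptom or condition, whatever its severity, with approximate onset.
3. Record all medicines taken in the prior 30 days, not only those for asthma or severe disease.

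In section 8.6.4, state that the on-treatment AE and ADR summaries count only events that are new, or worse than the Visit 1 record, after the first dose. This gives the existing Appendix 1 exclusion something to be checked against. Reporting duties under section 10.1.1 need not change.

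The cost is one question and a few more eCRF lines at a visit that already collects history and medication. No visit, test or subject is added; the downside is a small amount of extra data entry. The change has to be in place before enrolment, because a pre-dose baseline cannot be recovered later.
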